## H. PROJECT MANAGEMENT PLAN

### H.1. Resources and Facilities Required

This team already has the majority of resources and facilities needed. We have identified the sites and have begun developing relationships with these locations.

### H.2. Overview of Administration Plan

The proposed study will be administered through the Durham HSR&D Center of Excellence. The investigators have an extensive history working together and hold various academic appointments in the Duke Division of General Internal Medicine, Departments of Psychiatry and Biostatistics and Bioinformatics, and School of Nursing at Duke University Medical Center and Department of Health Policy and Management in the School of Public Health at the University of North Carolina at Chapel Hill. Prior to beginning the study, IRB approval will be obtained.

### H.3. Anticipated Time Table for Funded Grant

We propose a **four-year** study. Work on how to select potential subjects, abstract appropriate data, developing training material has already occurred. There will be 6 months to hire and train staff, 15 months for enrollment, and 18 months of intervention follow-up. The final 9 months of the grant will be devoted to data analysis. The first 3 of these months will be devoted to examining clinical and adherence outcomes. Cost data analysis as well as preparing reports will occur in the final 6 months of the study.

**Table 5: Study Gantt Chart (i.e. anticipated study timeline during grant funding)**

	YEAR 1				YEAR 2				YEAR 3				YEAR 4			
	Q 1	Q 2	Q 3	Q 4	Q 1	Q 2	Q 3	Q 4	Q 1	Q 2	Q 3	Q 4	Q 1	Q 2	Q 3	Q 4
Project Start Up																
Higher Study Staff	X	X														
Train staff	X	X														
Finalizing computerized intervention modules	X	X														
Intervention Implementation																
Pilot process for enrolling patients ~ 10 patients			X													
Enrolling Patients in Intervention			X	X	X	X	X									
Delivery of 18-Month Intervention				X	X	X	X	X	X	X	X	X	X			
Data Analysis																
Planning for data analysis														X		
Data analysis and paper preparation															X	X

## **I. HUMAN SUBJECTS**

The study will be conducted according to Good Clinical Practice guidelines, the U.S. Code of Federal Regulations (CFR) Title 21 CFR (Part 16 – Protection of Human Subjects and Part 56 – Institutional Review Boards), VHA Handbook 1200.05, the Declaration of Helsinki, and other applicable regulations and laws. **This protocol will be submitted to the Durham VA Medical Center Institutional Review Board for approval.** The informed consent of each subject will be obtained in accordance with 21 CFR Part 50 and the Declaration of Helsinki before protocol-specified procedures are carried out.

**Informed consent and waiver of HIPAA authorization** will be obtained using an informed consent form and waiver of HIPAA authorization form that will be used after approval of the Durham VA Medical Center Institutional Review Board. A copy of the informed consent will be scanned into the VA electronic medical record.

### **I.1. Sources of Materials**

The procedures for obtaining research material for the study include anthropometric and BP measurements, medical records, interviews, and self-completed questionnaires. Trained and certified professional staff will obtain all data according to detailed study protocols. Data will be collected directly from study participants, medical records, and used specifically for research purposes.

### **I.2. Potential Risks**

**Blood pressure.** All participants will have HTN and receive regular medical care from clinics affiliated with the Durham VA Medical Center. The study intervention is likely to lower BP. However elevated BP or low BP may be noted by study personnel as a result of study measurements or home BP monitoring.

**Physical activity.** Patients receiving the disease management intervention are encouraged to increase their physical activity, raising the possibility of musculoskeletal injury or unmasking of heart disease.

**Food.** Participants receiving information through the diet phone call module will be encouraged to try new foods, raising the possibility of allergic reactions. In addition, participants will be encouraged to increase intake of dairy products, possibly leading to symptoms of lactose intolerance.

**Breach of patient confidentiality.** There is a small risk that unauthorized persons could get access to personal or study-related patient information.

### **I.3. Adequacy of Protection Against Risks**

The specific risks of participation in this study are noted above; procedures for protection follow. Study personnel will not be responsible for the clinical care of the participants and participants will be made aware of this delineation of responsibility. Participants will be referred to their primary provider if any clinical problem is detected.

#### **Blood Pressure.**

Certain extreme BP values, both high and low, carry an urgent risk of major complication. As a result, if the most recent BP measurement is reported during a patient phone call, at a study data collection visit, or during other contact between study clinical staff and a patient is at one of these extremes, we will advise patients to take specific actions to minimize those risks. For SBP  $\geq$  180 mmHg or DBP  $\geq$  110mmHg, we will advise the patient to contact her/his triage nurse (or other similar position) within 24-48 hours. If a patient is advised to contact the triage nurse, a note will be placed in the patient's medical record. For participants that have moved care to a different VA facility (as described in section C.3.b) we will advise patient to contact her/his triage nurse (or other similar position) but not put a note in their medical record. This level corresponds to JNC 7 classification of Stage 3 hypertension and are the safety criteria currently used by our data safety monitoring board in TCYB and TEACH-DM. For SBP  $\geq$  210 mmHg or DBP  $\geq$  120 mmHg, or SBP  $\leq$  90 mmHg and/or DBP

≤40, we will advise the patient to seek immediate care. For all instances in which we recommend seeking immediate care, we will put a note that requires PCP co-signature in the patient's medical record. For participants that have moved care to a different VA facility (as described in section C.3.b) we will advise patient to go to the emergency room or urgent care facility but not put a note that requires PCP co-signature in their medical record (because it is not possible to require co-signatures of providers from another facility).

**Physical Activity.** Risks from increased physical activity will be minimized by encouraging moderate rather than vigorous activity. If an exercise-related symptom is reported to the interventionist during phone calls, the interventionist advise participants to get clearance from their primary care provider before they can restart physical activity.

**Food.** Risks from trying new food as a result of diet suggestions will be minimized by encouraging individuals who have previously become sick after eating dairy products or other specific foods mentioned to patients not to resume eating such items without consulting their primary care provider. Further, patients will be told not to continue eating new foods if they become sick or experience an allergic reaction.

**Data Confidentiality.** The Durham HSR&D COE conducts computer operations in its secure Centralized Computing Facility managed by VA OI&T network and server administrators. In the Center's computing facility, all research data are stored on VA-Administered servers which are physically secured in a Durham VAMC server room. VA network access to research data is controlled in accordance with the Center's Standard Operating Procedures and VA policies and in cooperation with the Durham VAMC IRB. The utilization data will be downloaded directly from national files to the VA network and servers administered by the Durham HSR&D COE. The master's statistician will have exclusive access to these files and they will not be moved from this secured folder and network environment.

Confidentiality will be assured through several mechanisms. First, each participant will be assigned an anonymous study ID which will be used on all study forms. Second, all study records that contain participant information will be kept in secured, locked areas when not in use. In addition, such materials, when in use, will be kept away from public scrutiny. Third, access to all participant data and information will be restricted to authorized personnel. In the case of computerized study data, access to data will be password protected, and staff members will be assigned individualized passwords and permissions that allow them access to only those elements of the data management system to which they are authorized. In addition, all study personnel will maintain certification with the Durham VAMC IRB that they have completed training in research ethics and confidentiality. Finally, participants will not be identified by name in any reports or publications, nor will data be presented in such a way that the identity of individual participants can be inferred.

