#### **C.3.b. Inclusion Criteria Determined During Initial Screening Phone Call with Potential Subjects.**

Patients must indicate that they both:

- Have a VA or affiliated clinic provider that they consider to be their main PCP.
- Receive the majority of healthcare at the Durham VAMC (or affiliated clinic).

These inclusion criteria are used to ensure that patients in the trial consider themselves to be VA primary care patients who are receiving hypertension care in the VA. We conceive of this pragmatic trial as informing interventions that would be suggested by the PACT/PCMH model. Key to this model is the integration of patient-responsive services within a care team. Clinicians in this study will have the ability to communicate with the patients care team. This link to primary care differentiates the proposed program and eventual implementation from stand-alone disease management programs that may be provided by outside groups. Our approach is supported, by the PACT/PCMH and the Chronic Care Model. In a 2006 mailed survey of Durham VAMC patients with diabetes that we conducted, 17% respondents reported that they do not have a PCP at the Durham VAMC who provides the majority of their diabetes care. If a patient switches to another VA facility during our study we will no longer conduct monthly or bimonthly encounter calls but we will continue to schedule study follow up visits.

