### **C.19. Safety Parameters for Primary Outcome**

Certain extreme BP values, both high and low, carry an urgent risk of major complication. As a result, if the most recent BP measurement is reported during a patient phone call, at a study data collection visit, or during other contact between study clinical staff and a patient is at one of these extremes, we will advise patients to take specific actions to minimize those risks. For SBP  $\geq$  180 mmHg or DBP  $\geq$  110mmHg, we will advise the patient to contact her/his triage nurse (or other similar position) within 24-48 hours. If a patient is advised to contact the triage nurse, a note will be placed in the patient's medical record. For participants that have moved care to a different VA facility (as described in section C.3.b) we will advise patient to go to the emergency room or urgent care facility but not put a note that requires PCP co-signature in their medical record (because it is not possible to require co-signatures of providers from another facility). This level corresponds to JNC 7

classification of Stage 3 hypertension and are the safety criteria currently used by our data safety monitoring board in TCYB and TEACH-DM. For SBP  $\geq$  210 mmHg or DBP  $\geq$  120 mmHg, or SBP  $\leq$  90 mmHg and/or DBP  $\leq$  40, we will advise the patient to seek immediate care. For all instances in which we recommend seeking immediate care, we will put a note that requires PCP co-signature in the patient's medical record. For participants that have moved care to a different VA facility (as described in section C.3.b) we will advise patient to go to the emergency room or urgent care facility but not put a note that requires PCP co-signature in their medical record (because it is not possible to require co-signatures of providers from another facility).

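### For participants whose care has moved to another VA facility, C.19 and I.3 give different advice for the same reading at the 180/110 level

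*Protocol*

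**What the plan says.** C.19 and the Blood Pressure part of I.3 describe one procedure in nearly the same words. Both have two levels.

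- **Lower level, SBP ≥180 or DBP ≥110 mmHg.** For participants still in Durham care, C.19 says "we will advise the patient to contact her/his triage nurse (or other similar position) within 24-48 hours", and a note goes in the record. I.3 says the same.
- **Lower level, participants whose care has moved to another VA facility.** C.19 says "we will advise patient to go to the emergency room or urgent care facility but not put a note that requires PCP co-signature". I.3 says "we will advise patient to contact her/his triage nurse (or other similar position) but not put a note in their medical record".
- **Immediate-care level, SBP ≥210 or DBP ≥120, or SBP ≤90 and/or DBP ≤40 mmHg.** Both sections advise immediate care, with a note that the PCP must co-sign. For moved participants both name the emergency room or urgent care and drop the co-signed note.

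C.3.b explains why moved participants are still seen. If a patient switches to another VA facility, "we will no longer conduct monthly or bimonthly encounter calls but we will continue to schedule study follow up visits".

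**The concern.** Trigger and subgroup are identical in the two sections, but the advice differs in where the participant should go and how urgently. One section belongs to the methods and the other to the human-subjects protections. Staff working from one would depart from the other, and a monitor could not say which conduct complied with the protocol. The protocol itself describes such extreme readings as carrying urgent risk, so the instruction ought to be unambiguous even for a small group.

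**Working it through.** No arithmetic on sample size, power or event rates applies. The check compares the two sections level by level.

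| Situation | C.19 | I.3 | Agree? |
|---|---|---|---|
| SBP ≥180 or DBP ≥110, still in Durham care | Triage nurse in 24-48 hours; note | Triage nurse in 24-48 hours; note | Yes |
| SBP ≥180 or DBP ≥110, care moved | Emergency room or urgent care; no note needing PCP co-signature | Triage nurse; no note | **No** |
| Immediate-care level, still in Durham care | Immediate care; co-signed note | Immediate care; co-signed note | Yes |
| Immediate-care level, care moved | Emergency room or urgent care; no note needing PCP co-signature | Emergency room or urgent care; no note needing PCP co-signature | Yes |

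**Is the C.19 sentence attached to the lower level?** Yes. It follows the 180/110 rule and stands directly before the sentence beginning "This level corresponds to JNC 7". The 210/120 level is introduced only after that, with its own moved-care sentence. I.3 has the same order. The disagreement does not come from reading a higher-level sentence at the wrong level.

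**Which readings are affected?** Those that meet the lower trigger but not the immediate-care trigger:

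- lower trigger: SBP ≥180 or DBP ≥110;
- immediate-care trigger: SBP ≥210, or DBP ≥120, or SBP ≤90, or DBP ≤40;
- lower trigger without immediate-care trigger, in whole mmHg: SBP 180 to 209 with DBP 41 to 119, or DBP 110 to 119 with SBP 91 to 209.

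**Can the case arise?** Yes. C.3.b stops the encounter calls but keeps the follow-up visits. C.18 measures blood pressure at those visits, and both safety sections apply at study data collection visits. After baseline there are at most three per participant (6, 12 and 18 months).

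**Are the note rules incompatible?** Not strictly. C.19 excludes only a note needing PCP co-signature, and I.3 excludes any note. C.19's general note rule is tied to advice to contact the triage nurse, which is not its advice to moved participants, so it does not require a note for them. Entering none meets both sections. An ordinary note without co-signature would be allowed by C.19 and barred by I.3.

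**Does anything else settle the matter?** No part of the protocol gives one section precedence over the other.

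**The case against.** The best case against the point is that it is small. C.3.d excludes patients who plan to leave the area or will not attend Durham visits, so few should move. Those who do have care at the new facility, and I.3 states that study personnel are not responsible for clinical care and refer problems to the primary provider. Both versions send the participant to clinical attention. C.19 also repeats its moved-care sentence at both levels, co-signature reasoning included, although its lower-level note mentions no co-signature. That looks like an editing slip between near-duplicate sections. These arguments limit the weight of the point but do not remove the conflict, and a slip would not show which instruction was meant.

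A reader might infer more than the text supports:

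- **That every reading at or above 180/110 in a moved participant is in conflict.** It is not: from SBP 210 or DBP 120 upward, and at the low limits, the sections agree.
- **That the instructions are opposite.** They differ in destination and urgency; neither withholds advice.
- **That the documentation rules cannot both be met.** They can, by entering no note.
- **That this rule is the main safeguard for these participants.** The risk questions in C.14 and I.5 are tied to scheduled interventionist encounters, and the encounter calls stop, so the rule does matter at study visits. To call it the main safeguard is still an inference, given the care available elsewhere.

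**Conclusion.** The point holds as an internal inconsistency in a safety instruction. It is confined to participants whose care has moved to another VA facility and to readings that reach SBP ≥180 or DBP ≥110 but not the immediate-care limits. For those readings the action differs between C.19 and I.3, and the note wording differs in scope only.

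The size is expected to be small. The protocol does not say how many of the 400 participants will move or how many readings will fall in this range, so that few are affected is a reasonable expectation and not a stated figure. The primary outcome, its analysis and the sample size do not depend on which instruction is followed. The thresholds are the same in both sections, so the C.9.c escalation rule that refers to C.19 is not put in doubt either. The conclusion rests only on the wording and order of the two sections. The documents do not show which action was intended, and no view is taken on that. Correction is worthwhile because the instruction concerns patient safety and the remedy is simple.

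**What to change.** Reconcile C.19 and I.3 so that both state the same action and the same documentation rule for moved participants at the 180/110 level below the immediate-care limits. The study physicians should decide which action and which rule apply. The documentation rule should say plainly whether any note is to be entered, or only that no co-signature is sought. One section could then refer to the other instead of restating the procedure, which would prevent the texts from drifting apart again. The cost is a wording amendment; design, data collection and analysis do not change.

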#### **I.4. Anticipated Adverse Events**

Because of the increased risk of these patients for cardiovascular and other diseases, it is expected that these patients will have a variety of episodes related to cardiovascular and related diseases such as diabetes. Such complications would be expected to occur in the absence of the intervention. These may include, but are not limited to, heart attack, stroke, and complications of diabetes among those patients with the disease. Because of the advanced age of many patients enrolled in clinical trials in the VA setting, it can be expected that other conditions related to aging may occur that would occur without the presence of the intervention. This includes, but is not limited to, the diagnosis of cancer and dementia. Further, while patients will be encouraged to not smoke and limit alcohol intake, those patients who smoke, drink alcohol, or take illicit drugs would be expected to have related complications. This includes, but is not limited to, development of disease of the lung or liver.

#### **I.5. Procedures for Assessing Immediate Patient Risks.**

During each scheduled encounter between a patient and study interventionist, immediate patient risks will be assessed via brief clinical questions asked by the interventionist. Emergent concerns will require referral to emergency care for immediate medical attention, usually by having the patient call 911. These include active chest pain, typical cardiac chest pain of duration > 10 minutes within the last 24 hours, dyspnea, SBP ≥ 220

mmHg, DBP  $\geq$  120 mmHg, SBP  $\leq$  90 with lightheadedness, heart rate  $\geq$  120, heart rate  $\leq$  50 with lightheadedness, new severe generalized or focal weakness, and altered mental status. In response to all other concerns not related to blood pressure the patient will be urged to contact his/her PCP.

#### **I.6. Potential Benefits to Subjects and Others.**

Potential benefits for study participants include improved lifestyle, improved control of BP, and consequent reduction in cardiovascular risk. An additional benefit for some participants may be personal satisfaction in being part of a study that may have major public health implications for the VA and community. No benefit from participation can be guaranteed. Potential benefits to others include the possibility that this research will lead to a better understanding of how to match resources for disease management programs to the clinical needs of patients.

#### **I.7. Importance of Knowledge to be Gained.**

The proposed research would examine whether a disease management program that is titrated by matching the intensity of resources to patients' disease control leads to superior outcomes compared to a low-intensity management strategy. Using a pragmatic clinical trial, this study would provide important evidence of a clinically-sensible disease management program that has the potential for widespread implementation, especially as the VA adopts the patient-centered medical home.

#### **I.8. Data and Safety Monitoring Plan.**

During the course of the study the investigators will monitor the integrity of data collection and monitor for adverse events. We do not anticipate any real harm to patients, but adverse event forms will be used to report all unanticipated events. The following information will be included in the report: date of event, attribution to intervention, and outcome of adverse events. Death will be reported within 24 hours. Unanticipated adverse events will be reported within 5 business days. Reports will be submitted via overnight courier or facsimile to the Durham VAMC IRB and VA HSR&D. A written follow-up will be submitted within 30 calendar days. All adverse events (serious or not, related or unrelated, anticipated or unanticipated) will be reported in the annual report to the Durham VAMC IRB and VA HSR&D.

#### **I.9. Inclusion of Women.**

The study has a target of enrolling until we randomizing 400 patients. The 400 number is based on the potential number of patients to be randomized. The intervention will be delivered to both male and female patients. There will be no inclusion/exclusion criteria based on gender. Approximately 8% of primary care patients at the Durham VAMC are women. We expect that this will be the approximate percentage of female patients that will be enrolled in the study.

